Reoperation for TR: The difference in the rate of requiring subsequent TV annuloplasty after the initial MVS will be compared between randomization groups. Reoperation for TR may not occur because death from any cause precedes the event; thus, it is possible that censoring patients at all-cause mortality will lead to biased estimates when analyzing time to first event. Therefore, competing risks analysis using the methods of Fine and Gray (1999) will be used to estimate group differences.

Degree of TR: Between group differences in the presence of severe TR at two years post randomization or, for patients enrolled with less than moderate TR, the progression by two grades will be compared using a two-tailed 0.05 level chi-squared test of the equality of two proportions.

MACCE: The proportion of patients experiencing major adverse cerebrovascular and cardiac events, defined as the composite event of death, stroke, and the serious heart failure events, is of particular interest. Given that this trial's primary endpoint is likely to be determined by echocardiographic assessments, it will be important to supplement the finding of a treatment effect (or lack of one) for the primary endpoint with a corresponding effect on a more clinical endpoint such as MACCE (and its component elements). As the trial is not powered to detect a difference in MACCE, a statistically significant treatment difference in MACCE is not expected; however, an observed difference in MACCE, consistent in direction with that observed for the primary endpoint will serve to validate the trial's findings. No matter the result, the interpretation of the trial's results will necessarily consider the difference in MACCE observed between treatment groups. The rate of major cerebrovascular or cardiac events will be compared between randomization groups over 24 months post-randomization using a Cox proportional hazards regression model. We expect MACCE two-year event rates to be approximately 15% for patients randomized to MVS alone. With a total of 400 patients randomized with equal allocation to MVS alone or to TR repair plus MVS, there is 90% power to detect an absolute decrease in MACCE to approximately 9-10% for patients randomized to TR plus MVS compared to MV surgery alone.

A number of additional secondary analyses are planned to supplement the primary analysis and aid interpretation of the trial's results.

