6. STATISTICAL METHODOLOGY

6.1 General Principles

Study day will be calculated from the reference start date, and will be used to show the study days of assessments and events. Reference start date is defined as the date of randomization unless otherwise specified. In analyses of index length of stay, index ICU days, peri-operative (30 day) mortality, and peri-operative (30 day) readmissions the reference date is

the date of surgery. In the situation where the event date is partial or missing, study day, and any corresponding durations are to appear partial or missing in listings. If a missing event date, such as a discharge date for a hospital readmission, is necessary to calculate patient-time at risk, the missing event date will be imputed using the median length observed for similar events.

Continuous variables will be summarized using the following descriptive statistics: number of non-missing values, means, standard deviations, medians, interquartile range, maximum, and minimum. Categorical variables will be summarized using number of non-missing values, counts and percentages.

Rates of events will be calculated as the ratio of the total number of events recorded divided by the total patient-time. Total patient-time will be calculated by summing the time (in study time units, e.g., days, months or years) that patients were at risk for a specific event from the reference time point until either study exit or the end of the time period of interest. Rates and 95% confidence intervals will be reported.

Time-to-event variables will be summarized using the Kaplan-Meier method or, in the presence of competing risk, the Gray method (Gray, 1988).

For any variable measured at multiple points in time, change from baseline will be calculated as the difference between the value of the variable at a specific point in time (e.g. 1 year) minus the baseline value. Relative change from baseline will be calculated as the value of a parameter at a specific point in time minus the baseline value of the parameter divided by the baseline value of the parameter. Percent change will be calculated as the relative change multiplied by 100.

All hypothesis testing will be conducted at the 0.05 two-sided significance level unless otherwise specified. P-values will be rounded to three decimal places. P-values less than 0.001 will be reported as <0.001 in tables. P-values greater than 0.999 will be reported as >0.999.

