6.5.2 Analyses of Secondary Clinical Endpoints

6.5.2.1 Clinical and Functional Outcomes

MACCE: The rate of major cerebrovascular or cardiac events (defined as the

composite event of death, stroke, and serious heart failure events) will be compared between randomization groups over 24 months post-randomization using a Cox proportional hazards regression model.

Reoperation for TR: The difference in the rate of requiring subsequent TV annuloplasty after the initial MVS will be compared between randomization groups over 24 months post-randomization. Reoperation for TR may not occur because death from any cause precedes the event; thus, it is possible that censoring patients at all-cause mortality will lead to biased estimates when analyzing time to first event. Therefore, competing risks analysis using the methods of Fine and Gray (Fine & Gray, 1999) will be used to estimate group differences.

NYHA: The distribution of NYHA at 30 days, 6, 12 and 24 months will be presented for each randomization arm and compared using chi-squared tests.

Diuretic Use: The distribution of diuretic use at 30 days, 6, 12 and 24 months will be presented for each randomization arm and compared using chi-squared tests.

Six Minute Walk: Differences between groups in the distances travelled during the 6MWT at 30 days, 6, 12 and 24 months will be compared using Wilcoxon Rank-Sum tests.

Gait Speed Tests: Differences between groups in gait speed at 12 and 24 months will be compared using Wilcoxon Rank-Sum tests.

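### The protocol lets a MACCE difference that merely points the same way as the primary endpoint count as validation, a standard met about half the time when repair has no effect on MACCE

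*Protocol*

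**What the plan says.** The passage is the MACCE paragraph of the protocol's Analytical Plan, under Analyses of Secondary Endpoints. It expects the primary endpoint to be settled mainly by echocardiography and says a more clinical endpoint is needed beside it. It describes the trial as not powered for MACCE and adds that "a statistically significant treatment difference in MACCE is not expected". It then states that "an observed difference in MACCE, consistent in direction with that observed for the primary endpoint will serve to validate the trial's findings". The next sentence says that interpretation will take the MACCE difference into account whatever the result.

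The same paragraph gives the planning figures: "We expect MACCE two-year event rates to be approximately 15% for patients randomized to MVS alone". For the planned 400 patients, split equally between the arms, it claims that "there is 90% power to detect an absolute decrease in MACCE to approximately 9-10" per cent. MACCE is to be "compared between randomization groups over 24 months post-randomization using a Cox proportional hazards regression model".

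SAP section 6.5.2.1 defines MACCE as the "composite event of death, stroke, and serious heart failure events" and specifies the Cox comparison. It contains neither the validation sentence nor the power figure. SAP section 6.1 sets the general rule: "All hypothesis testing will be conducted at the 0.05 two-sided significance level unless otherwise specified".

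**The concern.** MACCE is the planned bridge from TR grade to patient benefit. The protocol's justification of the primary endpoint explains that a purely clinical endpoint was ruled out by low event rates and limits on sample size. What MACCE must show before the trial may call its finding clinically validated therefore matters.

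The only condition written down is agreement in direction. A hazard ratio of 0.99 meets it as well as 0.60 does. The two composites also share death, so their directions are positively correlated by construction and MACCE is not an independent check. A primary result driven by TR grade alone could be published as validated when repair did nothing for MACCE, or slightly worsened it without the sample showing so.

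**Working it through.** **Inputs.** From the protocol: 200 per arm; MACCE 15% on MVS alone, with an alternative of 9–10%; primary endpoint 25% versus 12%; final critical value 1.969. From the SAP: two-sided 0.05. Assumed: two-year mortality of 2–8%, because the documents give no figure, and non-fatal MACCE events independent of non-fatal primary events within a patient.

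**1. The paragraph's own figure: 90% power for 15% versus 9–10%.**

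Power = Φ[(d − 1.96·SE0)/SE1], with d = 0.15 − p, SE0 = √(2·p̄(1 − p̄)/200) where p̄ is the mean of the two rates, and SE1 = √(0.15·0.85/200 + p(1 − p)/200).

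| Repair-arm rate p | d | SE0 | SE1 | Power |
|---|---|---|---|---|
| 9% | 0.060 | 0.0325 | 0.0324 | 45.5% |
| 9.5% | 0.055 | 0.0328 | 0.0327 | 38.8% |
| 10% | 0.050 | 0.0331 | 0.0330 | 32.7% |

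The 90% is not reproduced. Schoenfeld's formula for the Cox test (48–50 events, hazard ratio 0.58–0.65) gives 33–47%. A one-sided 0.05 test gives 45–60%. Power of 90% would need about 1,230 patients (for 9%) to 1,836 (for 10%), or with 400 patients a fall to about 5.2%. As a check on the method, the same formula gives 92.0% for the primary endpoint. It gives 88.4% with critical value 1.969 and 3% crossover, in line with the protocol's approximate 90%.

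**2. How often the directions agree by MACCE counts alone.** For independent counts C ~ Bin(200, 0.15) and T ~ Bin(200, p), the exact P(T < C) is:

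| True repair-arm MACCE | P(fewer in repair arm) | P(tie) |
|---|---|---|
| 15% (no effect) | 47.2% | 5.6% |
| 17% | 26.9% | 4.7% |
| 18% | 19.0% | 3.9% |
| 20% | 8.3% | 2.2% |
| 10% | 92.6% | 1.9% |
| 9% | 96.3% | 1.1% |

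On the hazard-ratio scale that the plan uses, ties practically vanish and the no-effect figure is about 50%. The normal approximation for 18% gives Φ(−0.03/0.0370) = 21%.

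As evidence for a fall to 9–10% against no effect, agreement carries a likelihood ratio of about 0.926/0.472 = 2.0 to 0.963/0.472 = 2.0. It only doubles the odds.

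**3. Agreement given the primary result, with shared deaths.** Deaths were simulated once per arm and counted in both composites.

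- Primary truly 25% versus 12% and significant, no MACCE effect: strict agreement in 48–50% of trials for mortality of 2–8%.
- No effect on either endpoint, primary significantly favouring repair by chance: about 55%, 59%, 67% and 79% for mortality of 2%, 3%, 5% and 8%.

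The second case first needs a chance-positive primary, which occurs in about 2.5% of null trials. The joint probability is therefore about 0.025 × 0.55 = 1.4% to 0.025 × 0.79 = 2.0%.

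**4. Precision.** With about 60 MACCE patients (15% of 400), SE(log HR) ≈ 2/√60 = 0.258. A hazard ratio of 1.0 would have a 95% CI of exp(±1.96 × 0.258), about 0.60 to 1.66. An estimate just below 1 satisfies the sentence while leaving substantial harm compatible with the data.

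**The case against.** The strongest reply is that nothing formal rests on this sentence. The trial's conclusion comes from the primary Wald test. The same paragraph calls MACCE supplementary, disclaims power for it and promises to consider it whatever the result. The SAP, whose stated purpose is to set out the analyses for publication, omits the sentence. Much of the component reporting also exists already: the protocol mentions MACCE's component elements, mortality has its own Cox analysis, and individual serious adverse events and heart failure readmissions are compared separately.

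All of that is accurate, and it limits the point to interpretation. It does not remove it. The sentence states in advance what result earns the claim of validation. Promising to consider MACCE in any case adds no criterion, and the SAP supplies none in its place.

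A reader might infer more than the documents support:

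- That the sentence is a test which inflates the trial's false-positive rate. It is not: it adds no positive primary results.
- That an observed MACCE excess could be called validation of a favourable primary result. It could not: opposite directions fail the condition. Only true harm that the sample happens not to show would pass.
- That agreement is worthless. It is not: it occurs in 93–96% of trials under the protocol's alternative, against about 47% under no effect.
- That MACCE should count as support only if its CI excludes 1. With 33–45% power, that would label a true fall to 9–10% inconclusive in about 55–67% of trials.

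**Conclusion.** The point holds as one of interpretation. The protocol attaches the word validate to agreement in direction alone, which occurs in about 47% of trials (about 50% on the hazard-ratio scale) when repair does not affect MACCE, and in about 19% when repair raises it from 15% to 18%. These figures use only the protocol's 15% and 200 per arm, with the 18% chosen for illustration. The 55–79% after a chance-positive primary result rests in addition on the assumed 2–8% mortality and on independence of the non-fatal events. The primary test and its error rate are untouched; what is affected is the clinical claim the trial may attach to its result.

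Separately, the 90% power figure contradicts the paragraph's own statement that the trial is not powered for MACCE, and recomputes to about 33–45% (two proportions, two-sided 0.05). It lies closer to the 93–96% chance of merely seeing the right direction, but the documents do not show where it came from.

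**What to change.** In the protocol's MACCE paragraph, delete the clause that a difference in the same direction will validate the findings. Replace it with text such as:

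> MACCE will be reported as a hazard ratio with its 95% confidence interval and treated as supportive evidence only. The interpretation will state which benefits and which harms the interval leaves compatible with the data. Because death is also part of the primary endpoint, the non-fatal MACCE components will be shown separately beside the composite.

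Put the same text in SAP section 6.5.2.1. Do not make statistical significance a condition. In the same edit, restate the MACCE power as about 33–45% for a fall from 15% to 9–10%, or delete the figure.

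The cost is one paragraph in the protocol and a few lines in the SAP, with no change to data collection, sample size or the primary analysis. The downside is that a favourable but imprecise MACCE result could no longer be cited as validation.

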We propose considering increasing sample size should the observed primary endpoint event rate among patients randomized to no repair of the TV be appreciably less than the assumed rate of 25%. The planned sample size of 400 patients has been determined to ensure that power is at least 90% to detect a 52% relative reduction of “failure” for patients randomized to tricuspid repair compared to no repair. Should the “failure” rate among controls be 20%, 400 patients provides approximately 83% power to detect a 52% relative reduction; for a 15% “failure” rate among controls there is approximately 70% power to detect a 52% relative reduction. Therefore, we suggest that the primary endpoint event rate be examined in control patients, using the same analysis set to be used for the interim analysis, and that the sample size be increased by up to 100 additional patients in order to maintain 80% power under the original alternative hypothesis for control rates as low as 15%. If no interim analysis is conducted or accrual is complete at the time of the first interim analysis, the sample size re-estimation will not be considered.

Assessment of Balance of the Randomization

The success of the randomization procedure in balancing important covariates between randomization groups will be assessed at the interim analysis and at the final analysis. Continuous measures will be compared using t-tests, while chi-squared tests will be used to compare categorical variables. As 400 patients will be randomized, no substantial imbalances are expected. However, should any covariate differ significantly between treatment groups at the 0.01 level, and be substantively large, we will adjust for those covariates in a secondary analysis of the primary endpoint.

Additional analysis of the primary endpoint

A subgroup analysis of the primary endpoint will be performed with subgroups defined by whether or not patients received a CABG procedure during the initial surgery. This analysis will be performed in the same manner as that described for the primary analysis.

Analyses of Secondary Endpoints

Individual components of the primary endpoint

Mortality: Differences in the rate of mortality between randomization groups over the first 24 months and the planned 60 months of follow-up will be assessed using Cox proportional hazards regression.

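### The protocol claims 90% power for a MACCE fall from 15% to 9-10% with 400 patients; the power is about 33-47%

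*Protocol*

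**What the plan says.** The MACCE paragraph of the protocol (Analytical Plan, Analyses of Secondary Endpoints) gives almost every input to a power calculation.

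- Control rate: "We expect MACCE two-year event rates to be approximately 15% for patients randomized to MVS alone".
- Sample size: "With a total of 400 patients randomized with equal allocation to MVS alone or to TR repair plus MVS".
- Claim: "there is 90% power to detect an absolute decrease in MACCE to approximately 9-10% for patients randomized to TR plus MVS".
- Analysis: rates are compared "over 24 months post-randomization using a Cox proportional hazards regression model".

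Earlier in the same paragraph the protocol says: "As the trial is not powered to detect a difference in MACCE, a statistically significant treatment difference in MACCE is not expected". It adds that a MACCE difference "consistent in direction with that observed for the primary endpoint will serve to validate" the trial's findings.

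The protocol's Sample Size Re-estimation section considers the primary endpoint at a 15% control rate, again with 400 patients, and says "there is approximately 70% power to detect a 52% relative reduction".

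The MACCE paragraph states no significance level. SAP section 6.1 supplies one: "All hypothesis testing will be conducted at the 0.05 two-sided significance level unless otherwise specified". The SAP's own MACCE text (section 6.5.2.1) keeps the Cox model and gives no power figure.

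**The concern.** Two statements in the protocol cannot be squared with 90% power.

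1. A 52% relative reduction from 15% takes the rate to 7.2%, a larger effect than a fall to 9-10%. The protocol gives that larger effect about 70% power with the same number of patients. A smaller effect from the same base rate cannot have more power.
2. A trial with 90% power for an effect its authors thought worth naming would not also be described as not powered for that endpoint.

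MACCE is the clinical endpoint that the protocol singles out to supplement a primary result expected to be driven mainly by echocardiography, and it says interpretation will take the MACCE difference into account whatever the result. A reader who trusts the 90% could take a non-significant MACCE comparison as good evidence against a benefit of 5 to 6 percentage points. In fact the trial would miss a benefit of that size more often than not.

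**Working it through.** **Inputs.** Control rate p1 = 0.15, alternative p2 = 0.09 to 0.10, and n = 200 per arm (protocol, MACCE paragraph). Two-sided alpha of 0.05, so z = 1.960 (SAP 6.1; the protocol's Sample size section uses the same level for the primary endpoint). No dropout is assumed, which favours the protocol's figure.

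**Chi-squared formula.** With p̄ = (p1 + p2)/2,

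power = Φ{ [ |p1 − p2| − 1.960·√(2p̄(1 − p̄)/n) ] / √[ (p1(1 − p1) + p2(1 − p2))/n ] }

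**The protocol's other power figures are reproduced first, at n = 200 per arm.**

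| Comparison | Protocol states | Computed |
|---|---|---|
| 25% v 12% | approximately 90% | 92.0% |
| 20% v 9.6% | approximately 83% | 83.6% |
| 15% v 7.2% | approximately 70% | 70.1% |

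The formula therefore agrees with the protocol's method everywhere except in the MACCE sentence.

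**MACCE, 15% v 9%.** p̄ = 0.12. Null standard error = √(2 × 0.12 × 0.88/200) = 0.0325. Alternative standard error = √[(0.1275 + 0.0819)/200] = 0.0324. Power = Φ[(0.06 − 1.960 × 0.0325)/0.0324] = Φ(−0.114) = 45.5%.

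**MACCE, 15% v 10%.** p̄ = 0.125. Null standard error = 0.0331; alternative standard error = 0.0330. Power = Φ[(0.05 − 1.960 × 0.0331)/0.0330] = Φ(−0.449) = 32.7%.

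**Schoenfeld formula, for the Cox model.** Under proportional hazards, HR = ln(1 − p2)/ln(1 − p1). Expected events D = 200(p1 + p2). Power = Φ[ (√D/2)·|ln HR| − 1.960 ].

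- To 9%: HR = 0.580, D = 48. Power = Φ(3.464 × 0.544 − 1.960) = Φ(−0.075) = 47.0%.
- To 10%: HR = 0.648, D = 50. Power = Φ(3.536 × 0.433 − 1.960) = Φ(−0.428) = 33.4%.

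| Fall from 15% to | Chi-squared | Schoenfeld |
|---|---|---|
| 9% | 45.5% | 47.0% |
| 9.5% | 38.8% | 40.0% |
| 10% | 32.7% | 33.4% |

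Exact enumeration of the chi-squared test gives 45.5% and 32.6% at 9% and 10%, so the normal approximation is not the cause.

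**What 90% power would take.**

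- With 400 patients: a fall to 5.3% (chi-squared; 9.7 points) or 5.8% (Schoenfeld; 9.2 points).
- For a fall to 9%: about 615 (chi-squared) or 592 (Schoenfeld) patients per arm. For a fall to 10%: about 918 or 896 per arm.
- With 200 per arm and a fall to 9-10%: a control rate of about 20-22%, not 15%.

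**Whether another setting rescues the figure.** The largest re-estimated trial (500 patients) gives 39-56%. A one-sided 0.05 test with 400 patients gives 45-60%. Neither approaches 90%.

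**The case against.** The arithmetic is hard to dispute; the serious objections concern weight.

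**The paragraph already warns the reader.** It says the trial is not powered for MACCE before the power sentence appears, and its supporting criterion is the direction of the difference, not significance. No decision rule uses the figure and the SAP does not repeat it. This stands, and it limits the consequence. It does not make the sentence correct: the paragraph now makes two incompatible statements.

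**It is probably one wrong word.** The sentence speaks of an absolute decrease. A decrease *of* 9 to 10 points, to 6% or 5%, has power of 83.8% to 91.8% by chi-squared and 87.9% to 95.4% by Schoenfeld, which brackets the stated 90%. This is plausible, but it is an inference. As printed, the sentence puts the detectable difference at 5 to 6 points when it exceeds 9.

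**The 70% figure belongs to another endpoint and another test.** True, but the comparison depends only on the base rate, the effect and the sample size. The change of test does not close the gap: Schoenfeld power for 15% v 7.2% is 73.5%, still well short of 90% for the larger effect.

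**The significance level is imported.** The MACCE paragraph gives none, so two-sided 0.05 is an assumption taken from elsewhere in the documents. Relaxing it to one-sided 0.05 leaves power at 60% or below.

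**Conclusion.** The concern holds. The stated 90% should be about 33-47%, so it overstates the power by a factor of roughly two (90/47) to nearly three (90/33). The result rests on a two-sided 0.05 level, no dropout and, for the Schoenfeld figures, proportional hazards over 24 months. Allowing for dropout would lower the power further.

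The sentence should be corrected, but the error is confined to it. MACCE is a secondary endpoint, and the primary analysis, the total of 400, the interim rule and the re-estimation rule do not depend on this figure. What is at risk is the reading of a non-significant MACCE result.

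**What to change.** Ask the sponsor to confirm the effect intended, then restate the sentence in the protocol's MACCE paragraph. Suggested content: with 400 patients and a two-sided 0.05 test, there is 90% power to detect an absolute decrease in MACCE *of* about 9 to 10 percentage points (from 15% to between 5% and 6%; 5.3% by chi-squared, 5.8% by Schoenfeld); power to detect a fall *to* 9-10% is about 33-47%. Giving the significance level in the sentence removes the need to import it.

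Keep the statement that the trial is not powered for MACCE; it then agrees with the rest of the paragraph. SAP section 6.5.2.1 needs no change.

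The cost is one sentence in the protocol, with no additional patients, data or analyses. The stated power for MACCE becomes less favourable.
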